### 10.7. PHYSICAL EXAMINATION

Physical examination are performed at baseline (within 7 days prior to study medication administration on Day 1 of Cycle 1), within 24 hours prior to study drug administration on Day 1 beginning with cycle 2, the end of treatment visit and 30-day safety follow-up visit. The physical examination data is presented in a data listing.

### 10.8. PERFORMANCE STATUS

ECOG performance status is recorded at baseline (within 28 days prior to study medication administration on Day 1 of Cycle 1), Day 1 of cycle 1 prior to first dose, within 24 hours prior to study drug administration on Day 1 beginning with Cycle 2, the end of treatment visit and 30-day safety follow-up visit.

ECOG Performance Status scores have 6 different grades from 0 to 5 and described in the following table:

Table 10: Eastern Cooperative Oncology Group

Sponsor: Taiho Oncology, Inc. Protocol: TPU-TAS-120-101

Version: 3.3, Phase 1 Dose Escalation Only

## Statistical Analysis Plan

GRADE	ECOG
0	Fully active, able to carry on all pre-disease performance without restriction.
1	Restricted in physically strenuous activity but ambulatory and able to carry out work of a light or sedentary nature, eg, light house work, office work.
2	Ambulatory and capable of all self-care but unable to carry out any work activities. Up and about more than 50% of waking hours.
3	Capable of only limited self-care, confined to bed or chair more than 50% of waking hours.
4	Completely disabled. Cannot carry on any self-care. Totally confined to bed or chair.
5	Dead.

The change from Day 1 in Cycle 1 in the ECOG Performance Status scores will be presented in a shift table by cohort and overall.

### 10.9. OPHTHALMOLOGICAL EXAMINATION

Ophthalmological examination will be performed at baseline (within 28 days prior to study medication administration on Day 1 of Cycle 1) and 4-6 weeks after the first dose. The examination will be repeated, if clinically indicated, and the repeat examination will include the same testing employed at baseline in addition to any other clinically indicated examination. Ophthalmological examination result will be listed.

#### 10.10. NEUROLOGICAL EXAMINATION

Neurological examination will be performed at baseline (within 28 days prior to study medication administration on Day 1 of Cycle 1). The basic neurologic examination will encompass testing of: cranial nerves II-XII, muscular strength of upper and lower extremities, deep tendon reflexes of upper and lower extremities. This examination will be repeated, if clinically indicated, and the repeat examination will include the same testing employed at baseline in addition to any other clinically indicated examination. Neurological examination result will be listed.

### 10.11. PREGNANCY TEST

If the patient is female and of child bearing potential, a serum or urine B-HCG pregnancy test will be performed 7 days prior to the first administration of the study drug. Pregnancy test result will be listed.

Sponsor: Taiho Oncology, Inc. Protocol: TPU-TAS-120-101

Version: 3.3, Phase 1 Dose Escalation Only

Statistical Analysis Plan

### 11. PHARMACOKINETICS

INC Research Biostatics Group is responsible for the calculation of pharmacokinetic parameters statistical analysis, production and quality control of TLFs of the PK data.

#### 11.1. SAMPLE COLLECTION

During Phase 1 Dose Escalation, blood samples for pharmacokinetic analysis will be collected at the following time points on Day 1 of Cycle 1 (C1D1) and on the last Wednesday of Cycle 1 (C1LW) (QOD arm) or on Day 1 of Cycle 1 (C1D1) and Day 21 of Cycle 1 (C1D21) (QD arm):

pre-dose (-0.5hr) and after the morning dose at 0.5 hr ( $\pm$  0.1 hr), 1 hr ( $\pm$  0.1 hr), 2 hr ( $\pm$  0.2 hr), 3 hr ( $\pm$  0.2 hr), 4 hr ( $\pm$  0.5 hr), 6 hr ( $\pm$  0.5 hr), 8 hr ( $\pm$  0.5 hr), 12 hr ( $\pm$  2 hr), 24 hr ( $\pm$  2 hr) (QOD and QD arms), and 48 hr ( $\pm$  2 hr) (QOD only).

The 48-hour postdose sample (QOD arm) and the 24-hour postdose sample (QD arm) must be collected prior to TAS-120 administration on that day.

During Phase 1 Dose Escalation, urine samples for pharmacokinetic analysis of TAS-120 will be collected on Day 1 of Cycle 1 (QOD arm) at the following time points:

pre-dose, 0 to 12 hr ( $\pm 2$  hr), 12 to 24 hr ( $\pm 2$  hr), and 24 to 48 hr ( $\pm 2$  hr).

The 24 to 48 hours postdose sample must be collected prior to TAS-120 administration on Day 3 and the last Friday of Cycle 1.

#### 11.2. PK PARAMETERS TO BE CALCULATED

The following PK parameters will be calculated for Day 1 of Cycle 1 (C1D1) and the last Wednesday of Cycle 1 (C1LW) in QOD arm, and for C1D1 and Day 21 of Cycle 1 (C1D21), according to the non-compartment method. AUC0-inf, MRT, CL/F and Vd/F will be calculated only for C1D1. Urine PK parameter will be calculated for only C1D1 in QOD arm. The calculated PK parameters will be summarized by study arm, dose levels and study periods.

## Plasma PK parameters:

- Cmax (ng/mL): Maximum concentration in plasma
- $T_{max}$  (hr): Time to reach maximum concentration in plasma
- $AUC_{0-last}$  (ng·hr/mL): Area under the concentration-time curve up to the last observable concentration

 $\mathsf{CC}$ 

Sponsor: Taiho Oncology, Inc. Protocol: TPU-TAS-120-101

Version: 3.3, Phase 1 Dose Escalation Only

## Statistical Analysis Plan

• AUC0-inf (ng·hr/mL): Area under the concentration-time curve up to infinity on C1D1 calculated as follows:

$$AUC_{0-inf} = AUC_{0-last} + C_{last}/\lambda z$$

where  $C_{last}$  is the last measurable plasma concentration and  $\lambda z$  is the elimination rate constant after the AM dose estimated using log-linear regression during the elimination phase. The points used in the  $\lambda z$  calculation will be determined by visual inspection of the data describing the elimination phase and at least three time points will be used in  $\lambda z$  calculations.

- AUC0-24 (ng·hr/mL): Area under the concentration-time curve up to 24 hours estimated as partial area (QD arm)
- AUC0-48 (ng·hr/mL): Area under the concentration-time curve up to 48 hours estimated as partial area (QOD arm)
- $T_{1/2}$  (hr): Terminal half-life time =  $ln(2)/\lambda z$
- MRT (hr): Mean residence time =  $AUMC_{0-inf}/AUC_{0-inf}$

where  $AUMC_{0-inf}$  is the area under the first moment curve (AUMC) extrapolated to infinity.

• CL/F (L/hr): Oral clearance = Dose/AUC0-inf

where the dose will be the actual dose per body of TAS-120.

• Vd/F(L): Apparent volume of distribution =  $(CL/F)/\lambda z$ 

RCmax: Accumulation ratio calculated based on Cmax

=  $C_{max}$  (C1LW or C1D21)/  $C_{max}$  (C1D1)

• RAUC: Accumulation ratio calculated based on AUC0-last

=  $AUC_{0-last}$  (C1LW or C1D21)/ $AUC_{0-last}$  (C1D1)

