## Statistical Analysis Plan

- Plasma concentrations below the LLOQ appearing in terminal samples will be treated as missing values;
- Plasma concentrations below the LLOQ in the middle of the curve that are flanked by measurable concentrations will be treated as missing values.

At the first dosing (C1D1), if the predose concentration is  $\leq 5$  percent of  $C_{max}$  value in that subject, the subject's data without any adjustments can be included in all pharmacokinetic measurements and calculations. If the predose value is > than 5 percent of  $C_{max}$ , the subject will be dropped from all PK evaluations.

The AUCs are calculated using noncompartmental analysis. The actual time of the plasma sample relative to the dosing time is used to calculate the AUCs. In calculating the AUCs a linear trapezoidal method is used for all portions of the plasma concentration-time curve. The AUC $_{0\text{-inf}}$  is calculated as the AUC $_{0\text{-last}}$  +  $C_{last}/\lambda z$  where AUC $_{0\text{-last}}$  is the area under the curve from 0 to the last quantifiable concentration,  $C_{last}$  is the last quantifiable concentration observed and  $\lambda z$  is the absolute value of the slope of the terminal log-linear phase.

The  $\lambda_Z$  will be calculated using the log-linear regression. Visual inspection and improvement in the adjusted RSQ will be used to determine those time points prior up to but not including the  $C_{max}$ . The elimination half-life  $(T_{1/2})$  is calculated as  $\ln(2)/\lambda_Z$ .

The parameter estimates for  $T_{1/2}$ ,  $AUC_{0-inf}$ , MRT, CL/F and Vd/F will not be calculated if ANY of the following conditions are met:

- Insufficient number of time points (less than 3) are available for calculating the slope of the log-linear regression line
- The adjusted RSQ is less than 0.81
- The percent of area extrapolated (time of last quantifiable plasma concentration to infinity) accounts for more than 20% of the  $AUC_{0-inf}$  ( $AUC_{0-inf}$  is less than 0.80).

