### 11.9. ACCUMULATION RATIO

Besides the calculation of individual accumulation ratio, the mean accumulation ratio at RP2D or MTD will be estimated by paired t-test. TAS-120 PK parameters ( $C_{max}$ , and  $AUC_{0-last}$ ) will be log-transformed and the mean ratio will be estimated for C1LW (C1LW/C1D1) and C1D21 (C1D21/C1D1).

Sponsor: Taiho Oncology, Inc. Protocol: TPU-TAS-120-101

Version: 3.3, Phase 1 Dose Escalation Only

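### The AUC accumulation ratio in the Phase 1 Dose Escalation SAP is built on AUC0-last, so it can compare unequal time spans and misstate accumulation in either direction when the last quantifiable time differs between the two days

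*SAP*

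**What the plan says.** All references are to the Phase 1 Dose Escalation SAP unless stated otherwise.

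- **The ratio.** Section 11.2 gives "R AUC : Accumulation ratio calculated based on AUC 0-last" and divides the value on C1LW (QOD) or C1D21 (QD) by the value on C1D1. Section 5.2 and the glossary use the same definition.
- **Its use.** Section 11.9 adds that "the mean accumulation ratio at RP2D or MTD will be estimated by paired t-test", on log-transformed Cmax and AUC0-last.
- **Where the area ends.** AUC0-last is the "Area under the concentration-time curve up to the last observable concentration". Section 11.5 states that "Plasma concentrations below the LLOQ appearing in terminal samples will be treated as missing values", so an unquantifiable tail moves the end point earlier, separately for each patient and day.
- **Clock and integration.** "The actual time of the plasma sample relative to the dosing time is used to calculate the AUCs", and "In calculating the AUCs a linear trapezoidal method is used for all portions of the plasma concentration-time curve".
- **Sampling.** Section 11.1 plans the same nominal times on both days. The 24 h and 48 h samples carry a ±2 h window, with the condition that "The 48-hour postdose sample (QOD arm) and the 24-hour postdose sample (QD arm) must be collected prior to TAS-120 administration on that day". Section 11.4 keeps out-of-window samples unless they overlap a neighbouring time point.
- **Fixed-interval areas.** Section 11.2 also defines AUC0-24 (QD) and AUC0-48 (QOD) as partial areas, for calculation on both days. They are not used for the ratio. The parameter list in 11.5 includes AUC0-24 but omits AUC0-48.
- **Protocol.** Section 12.2.4 asks for an accumulation ratio without naming the AUC.

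**The concern.** An accumulation ratio is meant to compare exposure over the same interval after the first dose and after repeated dosing. Here the upper limit of each area floats. Two identical concentration profiles can return a ratio other than 1 solely because the last sample was quantifiable on one day and not on the other, or because it was drawn a few hours later. The SAP contains no requirement for a common end time, no restriction to matched profiles and no sensitivity analysis for differing spans.

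At stake is the individual ratio for each patient and the mean ratio at the RP2D or MTD. Section 4.1 lists PK among the data on which the RP2D and schedule are chosen, so the summary should measure what its name says.

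**Working it through.** The documents state no accumulation ratio, so there is no figure to reproduce. The check asks how far the stated rule can move the ratio.

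**Inputs from the SAP.** QD sampling at 0, 0.5, 1, 2, 3, 4, 6, 8, 12 and 24 h, plus 48 h for QOD (11.1); linear trapezoid and actual times (11.5); ±2 h on the last sample (11.1).

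**Assumptions, not in the documents.** A one-compartment oral model with linear kinetics, ka = 1.5/h, and half-lives of 2 to 12 h. With k = ln 2 / half-life, and in units of dose over volume:

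- Day 1: C(t) = ka/(ka − k) × [exp(−kt) − exp(−ka·t)]
- Repeated QD dosing: the same expression, with the two exponentials divided by 1 − exp(−24k) and 1 − exp(−24ka) respectively

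**QD results.** Columns (a) to (c) are Day 21 over Day 1. Column (d) uses one identical profile on both days, sampled at 22 h on Day 1 and 26 h on Day 21.

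| Half-life (h) | (a) Both end at 24 h | (b) Both end at 12 h | (c) Day 1 ends 12 h, Day 21 ends 24 h | (d) 22 h vs 26 h only |
|---|---|---|---|---|
| 2 | 1.000 | 1.000 | 1.044 | 1.013 |
| 3 | 1.005 | 1.005 | 1.123 | 1.030 |
| 4 | 1.018 | 1.018 | 1.214 | 1.042 |
| 6 | 1.073 | 1.075 | 1.419 | 1.061 |
| 8 | 1.154 | 1.158 | 1.643 | 1.075 |
| 12 | 1.353 | 1.363 | 2.118 | 1.098 |

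For example, at a half-life of 8 h, Day 1 AUC0-12 is 7.18, Day 1 AUC0-24 is 10.23 and Day 21 AUC0-24 is 11.80. The fixed-interval ratio is 11.80/10.23 = 1.15. The AUC0-last ratio with the Day 1 24 h sample lost is 11.80/7.18 = 1.64.

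**No accumulation at all.** With identical profiles, a 12 h end on Day 1 and a 24 h end on Day 21 give 1.12, 1.32 and 1.42 at half-lives of 3, 6 and 8 h. For QOD with ends at 24 h and 48 h, the ratio runs from 1.00 (2 h) to 1.30 (12 h).

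**Opposite direction.** If the 24 h sample is available on Day 1 but lost on Day 21, the ratio is 0.81, 0.81 and 0.87 at half-lives of 6, 8 and 12 h, against true values of 1.07, 1.15 and 1.35. Reversing the window case in column (d) gives 1/1.098 = 0.91 at its extreme.

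**How narrow the trigger is.** By 24 h absorption is complete in this model, so the 24 h concentration rises from Day 1 to steady state by a factor 1/(1 − exp(−24k)):

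- 3 h: 1/(1 − 1/256) = 1.004
- 6 h: 1/(1 − 1/16) = 1.067
- 8 h: 1/(1 − 1/8) = 1.143

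Without variability, column (c) arises only if the quantification limit falls inside that rise of 0.4%, 6.7% or 14%. At 8 h the Day 1 value at 24 h is already 15.8% of Cmax, so the limit would have to lie above roughly 16% of Cmax.

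**The case against.** The strongest reply is that the large figures presuppose their own trigger. The nominal schedule is the same on both days, and columns (a) and (b) show that AUC0-last gives almost the right ratio whenever both days end at the same sample. Without within-patient variability the band that produces column (c) is narrow. Variability, or a sample simply missing on one day, would make discordance more common, but the documents give no basis for estimating how often. This stands, and it limits the figures to conditional illustrations.

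Three stronger readings are tempting and are not supported:

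- **That the ratio systematically exaggerates accumulation.** The error runs either way, as the reversed cases show.
- **That the estimate at the RP2D or MTD is therefore wrong.** Tail loss is most likely at low doses. Protocol 5.4 puts the QD RP2D at 20 mg, second highest of the QD doses evaluated (4, 8, 16, 20 and 24 mg), where an unquantifiable 24 h sample is less likely. MTD determination rests on dose-limiting toxicities (4.1.1), not on this ratio.
- **That dose-proportionality slopes will look steeper than 1.** Section 11.8 does use AUC0-last, and low doses would tend to lose their tails first, but no calculation here quantifies an effect on the slope. Those models also use Cmax, and AUC0-inf on Day 1.

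It is also fair that much would be visible from planned output. Individual concentrations and parameters are listed (11.7), Cmax accumulation is unaffected, and a reader given both partial areas could form the fixed-interval ratio. That helps a careful reader but does not correct the reported summary.

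Finally, a partial area to 24 or 48 h is hardest to obtain exactly when the last sample is unquantifiable or early, and the SAP has no rule for that case. This also stands, and the fix has to supply one.

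**Conclusion.** The definition is faulty as written: it does not guarantee equal intervals on the two days, and a fixed-interval alternative sits unused in the same section. The consequence is conditional. With a 24 h sample unquantifiable on Day 1 only, the ratio is 1.12 to 1.64 where 1.00 to 1.15 is correct (half-lives 3 to 8 h). The most extreme use of the sampling window alone gives at most about 1.10 (half-lives 2 to 12 h). With matched end points the effect is negligible. All of this rests on an assumed one-compartment model with ka 1.5/h; the quantification limit, the half-life and the frequency of discordant last samples are unknown.

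This is a secondary, descriptive PK measure. The case for changing it is that the change is cheap and makes the ratio interpretable, not that a trial decision is shown to be in error.

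**What to change.** 1. In sections 5.2, 11.2 and 11.9 and in the glossary, define the AUC accumulation ratio as AUC0-24(C1D21)/AUC0-24(C1D1) for QD and AUC0-48(C1LW)/AUC0-48(C1D1) for QOD. Run the log-scale paired analysis on these.
2. Add AUC0-48 to the parameter list in 11.5.
3. State the rule for short profiles. When the last quantifiable time is before 24 or 48 h, extrapolate the partial area with the terminal rate constant if it meets the 11.5 criteria. Otherwise form the ratio from the areas up to the last time point quantifiable on both days.
4. Keep the AUC0-last ratio as supportive.
5. As a secondary change for consistency, use AUC0-24 or AUC0-48 in the multiple-dose models of 11.8. Its effect on the slope has not been quantified.

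The cost is SAP wording plus a little extra analysis work, since both areas are already defined and the protocol does not prescribe which AUC to use. The downside is that some ratios will rest on extrapolation or on a shorter common interval; these should be flagged in the listing.

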#### Urine PK parameters:

Ae% (%): Urinary excretion rate as % of dose = Ae(total amount of excretion)/dose

• CLr (mL/min): Renal clearance = Ae(total amount of excretion)/AUC0-48

### 11.3. PLASMA AND URINE CONCENTRATION DATA

Plasma and urine concentration data will be assayed at Covance Laboratories Inc. as per the sample analysis outline of the bioanalytical study below.

CC

Sponsor: Taiho Oncology, Inc. Protocol: TPU-TAS-120-101

Page 49 of 64

Version: 3.3, Phase 1 Dose Escalation Only

## Statistical Analysis Plan

#### 11.4. PK SAMPLE COLLECTION TIME

03.007A.01

The calculation of PK parameter in plasma will be based on the actual time after the dosing. The values will be calculated as "actual clock time of blood collection" - "actual clock time of dosing" to obtain actual hours after dose. The actual time after dose will be summarized by study arm, dose levels and study periods according to nominal collection time. The urine PK parameters will be summarized according to nominal collection period, without any corrections with actual sampling time. The concentration data out of the time window will not be excluded from analysis unless the time point is overlapped with adjacent time points.

#### 11.5. CALCULATION OF PLASMA PK PARAMETERS

Estimation of pharmacokinetic parameters in plasma will be performed using Phoenix™ WinNonlin® (Certara, L.P.), Version 6.4 or later software.

The PK parameters of interest are  $C_{max}$ ,  $T_{max}$ ,  $AUC_{0\text{-last}}$ ,  $AUC_{0\text{-inf}}$  (C1D1 only),  $AUC_{0\text{-24}}$ ,  $T_{1/2}$ , MRT (C1D1 only),  $R_{Cmax}$ ,  $R_{AUC}$ , CL/F (C1D1 only), and Vd/F (C1D1 only). The  $C_{max}$  and  $T_{max}$  are obtained from experimental observations. If the maximum plasma concentration occurs at 2 or more time points, the  $T_{max}$  is assigned to the time of the earliest occurrence. In determining the  $T_{max}$ , the actual time of the plasma sample relative to the dosing time will be used.

The BLQ value will be handled as follows for the calculation of plasma PK parameters:

- The time of collection of the pre-dose sample will be set to zero;
- Actual post-dose sampling times are expressed relative to the time of dosing;
- Plasma concentrations below the LLOQ in the pre-dose sample(s) and in early time-points (lag-time) will be treated as zero, if applicable;

CCI

Sponsor: Taiho Oncology, Inc. Protocol: TPU-TAS-120-101

Version: 3.3, Phase 1 Dose Escalation Only

## Statistical Analysis Plan

- Plasma concentrations below the LLOQ appearing in terminal samples will be treated as missing values;
- Plasma concentrations below the LLOQ in the middle of the curve that are flanked by measurable concentrations will be treated as missing values.

At the first dosing (C1D1), if the predose concentration is  $\leq 5$  percent of  $C_{max}$  value in that subject, the subject's data without any adjustments can be included in all pharmacokinetic measurements and calculations. If the predose value is > than 5 percent of  $C_{max}$ , the subject will be dropped from all PK evaluations.

The AUCs are calculated using noncompartmental analysis. The actual time of the plasma sample relative to the dosing time is used to calculate the AUCs. In calculating the AUCs a linear trapezoidal method is used for all portions of the plasma concentration-time curve. The AUC $_{0\text{-inf}}$  is calculated as the AUC $_{0\text{-last}}$  +  $C_{last}/\lambda z$  where AUC $_{0\text{-last}}$  is the area under the curve from 0 to the last quantifiable concentration,  $C_{last}$  is the last quantifiable concentration observed and  $\lambda z$  is the absolute value of the slope of the terminal log-linear phase.

The  $\lambda_Z$  will be calculated using the log-linear regression. Visual inspection and improvement in the adjusted RSQ will be used to determine those time points prior up to but not including the  $C_{max}$ . The elimination half-life  $(T_{1/2})$  is calculated as  $\ln(2)/\lambda_Z$ .

The parameter estimates for  $T_{1/2}$ ,  $AUC_{0-inf}$ , MRT, CL/F and Vd/F will not be calculated if ANY of the following conditions are met:

- Insufficient number of time points (less than 3) are available for calculating the slope of the log-linear regression line
- The adjusted RSQ is less than 0.81
- The percent of area extrapolated (time of last quantifiable plasma concentration to infinity) accounts for more than 20% of the  $AUC_{0-inf}$  ( $AUC_{0-inf}$  is less than 0.80).

### 11.6. CALCULATION OF URINE PK PARAMETERS

The urine PK parameters will be determined for TAS-120 on C1D1. The amount of TAS-120 excreted in each urine collection will be calculated by multiplying the volume (in mL) by the concentration. Total amount of urinary excretion from time zero to 48 hours postdose (Ae mg) for TAS-120 will be calculated by summing the excretion values over all urine collections following a dose of study drug. Urinary excretion will be reported as a percentage of the administered dose of study drug (Ae%).

Sponsor: Taiho Oncology, Inc. Protocol: TPU-TAS-120-101

Version: 3.3, Phase 1 Dose Escalation Only

## Statistical Analysis Plan

Renal clearance of TAS-120 will be calculated as below.

• CLr (Renal clearance) = Ae(Total amount of excretion)/AUC0-48  $\times$  10^6  $\times$  60

The urine volume, urinary concentration, Ae (mg) Ae% and CLr of TAS-120 will be summarized by study arm and dose levels according each urine collection period.

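### The renal clearance formula in the Dose Escalation SAP multiplies by 60 where its own units require division by 60, so CLr as written is 3600-fold too high

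*SAP*

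**What the plan says.** All the relevant text is in the Dose Escalation SAP.

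- **Formula.** Section 11.6 starts from "CLr (Renal clearance) = Ae(Total amount of excretion)/AUC" over 0 to 48 hours and then adds conversion factors. In full it gives "CLr (Renal clearance) = Ae(Total amount of excretion)/AUC 0-48 $\times$ 10 6 $\times$ 60". The 6 is an exponent, so the factors are 10^6 and 60, both shown with a multiplication sign.
- **Unit of CLr.** The urine parameter list in section 11.2 has "CLr (mL/min): Renal clearance = Ae(total amount of excretion)/AUC", with AUC0-48 as denominator and no conversion factors.
- **Unit of Ae.** Section 11.6 defines "Total amount of urinary excretion from time zero to 48 hours postdose (Ae mg) for TAS-120" as the sum over the urine collections.
- **Unit of AUC0-48.** The plasma parameter list in section 11.2 has "ng·hr/mL): Area under the concentration-time curve up to 48 hours estimated as partial area (QOD arm".
- **Scope.** Section 11.2 states "Urine PK parameter will be calculated for only C1D1 in QOD arm".

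CLr also appears as a QOD-arm parameter in section 5.2 of this SAP and in section 12.2.4 of the protocol. Section 11.6 summarises it by study arm and dose level.

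**The concern.** A conversion formula can be checked against its units, and this one does not pass. The 10^6 is exactly the mg-to-ng conversion, so the formula was evidently built for the units stated in 11.2 and 11.6. The factor 60 can then only be the hour-to-minute step, and it is applied in the wrong direction.

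The planned controls might not catch this. Section 2.1 has the CRO perform the PK analysis according to this SAP, and the sponsor's preliminary results cover plasma samples only. Section 11.5 names WinNonlin for the plasma parameters, whereas 11.6 names no software for CLr, so the printed formula is the working specification. Section 18 relies on independent coding and electronic comparison, and two programmers coding the same formula would agree with each other.

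At stake is one reported parameter under the secondary PK objective. Its summary tables could also conflict with the oral clearance (CL/F) reported for the same patients.

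**Working it through.** **Inputs** (Dose Escalation SAP): Ae in mg (11.6); AUC0-48 in ng·hr/mL (11.2); CLr in mL/min (11.2); formula Ae/AUC0-48 × 10^6 × 60 (11.6).

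**Factor as written.** 10^6 × 60 = 6.0 × 10^7.

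**Factor required by the units.**
1. Ae (mg) × 10^6 = Ae in ng.
2. ng ÷ (ng·hr/mL) = mL/hr.
3. mL/hr ÷ 60 = mL/min.

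The required factor is therefore 10^6 / 60 = 1.667 × 10^4.

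**Ratio.** (10^6 × 60) / (10^6 / 60) = 60 × 60 = 3600. Ae and AUC cancel, so the ratio is the same for every patient and dose.

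**Illustration.** The documents give no Ae or AUC0-48 values, so all inputs in this table are assumed.

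| Ae (mg) | AUC0-48 (ng·hr/mL) | mL/hr | Correct mL/min | As written | Ratio |
|---|---|---|---|---|---|
| 1 | 1000 | 1000 | 16.67 | 60,000 | 3600 |
| 0.1 | 1000 | 100 | 1.67 | 6000 | 3600 |
| 0.01 | 2000 | 5 | 0.083 | 300 | 3600 |
| 0.001 | 1000 | 1 | 0.0167 | 60 | 3600 |

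**Other readings tried.**
- Both factors in the denominator, Ae/(AUC0-48 × 10^6 × 60): the result is 10^12-fold too low.
- Output meant in mL/hr: still 60-fold too high.
- Output meant in L/hr: 60,000-fold too high.
- Output meant in mL/s: 216,000-fold too high.

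None of these makes the formula correct.

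**Check against CL/F.** Section 11.2 defines CL/F as Dose/AUC0-inf, and renal clearance cannot exceed it. As written, CLr/(CL/F) = 3600 × (Ae/Dose) × (AUC0-inf/AUC0-48). AUC0-inf is at least AUC0-48, so reported CLr would exceed CL/F for any patient with Ae/Dose above 1/3600 = 0.028%. At lower excretion the inflated value may not exceed CL/F, and this comparison would then not reveal the error.

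**The case against.** **The symbol.** The finding turns on one operator in text extracted from a PDF, and mathematical characters are damaged elsewhere. The febrile neutropenia criterion in section 4.1.1 of the same SAP shows 8°C beside 100.4°F. In the Phase 2 SAP, the minus sign has gone from the treatment duration formula (6.5.1.1). A division sign misread as a multiplication sign cannot be excluded. However, the damage seen is mostly dropped characters rather than one operator replaced by another, and both operators here were read as the same sign. The caveat therefore stands as a reason to look at the source page first.

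**The reach.** CLr is calculated only for Cycle 1 Day 1 in the QOD arm, while the schedule taken forward is 20 mg QD. The MTD rests on dose-limiting toxicities (4.1.1). RP2D selection refers to PK data in general without naming CLr (4.1). Dose proportionality uses Cmax and AUC (11.8). No hypothesis or decision rule depends on CLr. All of this stands and keeps the point minor.

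**Safeguards.** Section 11.2 states the target unit, and section 18 includes review of program logic and outputs, so a careful programmer or reviewer could notice the conflict. That lowers the risk but does not correct the specification.

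**Stronger readings a reader might infer.**
- *Every CLr value would be physiologically impossible.* The documents give no Ae or CLr values. With an assumed Ae of 0.001 mg and AUC0-48 of 1000 ng·hr/mL, the formula returns 60 mL/min, which is wrong but not obviously impossible. Only the 3600-fold ratio is established.
- *The conclusion on renal elimination would be wrong.* Ae%, the share of dose recovered in urine, does not use this factor and still describes urinary recovery correctly.
- *Section 11.2 repeats the error.* It does not: it gives the plain ratio with the right unit.

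**Conclusion.** Wrong as written, minor severity. On the SAP's own units, the CLr formula in section 11.6 overstates renal clearance by exactly 3600-fold for every patient to whom it is applied. The factor is independent of the data and needs no outside source. The conclusion assumes only that the multiplication sign before 60 is what the source PDF prints. If the source shows division, there is no error. Whether any CLr output was actually produced with the printed formula cannot be told from the documents.

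**What to change.** 1. Look at the formula in section 11.6 in the source PDF. If it shows division by 60, nothing needs to change.
2. Otherwise replace it with: CLr (mL/min) = Ae (mg) × 10^6 / [AUC0-48 (ng·hr/mL) × 60].
3. If CLr has already been derived, check which formula was programmed. Rerun that one derivation and its summary and listing if the printed version was used.

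Section 11.2 needs no correction. The cost is one formula and, at most, one rerun, with no new data and no change to any other analysis.
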